A retrospective pre-post anti-IL-5/IL5R inhibitors treatment cohort study using the RESP database and the hospital charts including patients with severe asthma followed at the *Hôpital du Sacré-Coeur de Montréal* (Tertiary asthma clinic cohort).

Another retrospective pre-post anti-IL-5/IL5R inhibitors treatment cohort selected from the Quebec health administrative databases and reMed database (Population-based cohort).

Cohort entry will be defined as the first prescription of anti-IL-5/IL5R inhibitors filled on or after January 1, 2016 for both cohorts.

Outcomes

Objective 1, primary outcome: Response to anti-IL-5/IL5R inhibitors, defined by a reduction of asthma exacerbations of at least 50% and a 50% or higher reduction of the OCS doses in steroid dependent patients in the year following the initiation of anti-IL-5/IL5R inhibitors compared to the year prior to treatment initiation, in the tertiary asthma clinic cohort and in the population-based cohort.

Objective 1, secondary outcomes: Exacerbation rates and OCS doses (for steroid-dependent patients) in the year preceding and following initiation of anti-IL-5/IL5R inhibitors in the tertiary asthma clinic cohort and in the population-based cohort.

Objective 2: Response to anti-IL-5/IL5R inhibitors in the tertiary asthma clinic cohort and in the population-based cohort in the year following initiation of anti-IL-5/IL5R inhibitors.

Potential Predictors

Potential clinical response predictors to anti-IL-5/IL5R inhibitors in the Tertiary asthma clinic cohort are: age, sex, atopy, body mass index, smoking habits, percent predicted FEV₁, asthma treatment prescribed, blood eosinophil count, and sputum eosinophil count at cohort entry.

Potential clinical response predictors to anti-IL-5/IL5R inhibitors in the Quebec population (Population-based cohort) are: age, sex, type of asthma treatment filled in the year before treatment initiation with anti-IL-5/IL5R inhibitors adherence to ICS in the year before and after treatment initiation with anti-IL-5/IL5R inhibitors, exacerbation rate in the year before treatment initiation with anti-IL-5/IL5R inhibitors, and socio economic status (welfare recipients).

Source of data

The RAMQ database is formed of three files containing information on the patients' characteristics, medical services and prescribed medications. The RAMQ Patient file contains the patient's healthcare insurance number (HCIN), which is a unique patient identifier, and information on age, sex, birth date, area of residence, type of drug insurance plan, and date of death, if relevant. This file covers all Quebec residents. The RAMQ Prescription Medications file contains the HCIN and claims data on prescriptions filled at community pharmacies; for example, name, dose, form, quantity of medication dispensed, date & duration of the prescription, cost of medications, as well as the identification and the specialty of the prescribing physician for Quebec residents covered under the RAMQ's Public Drug Insurance Plan, about 42% of the population; these include persons receiving social assistance, persons not covered by a private drug plan, and about 90% of elderly. This file also contains the dates of coverage under the RAMQ's Public Drug Insurance Plan. The RAMQ Medical Services file contains the HCIN and claims data on medical services dispensed on a fee for service to all residents of Quebec in hospitals, emergency departments (ED) or medical clinics. Physicians are reimbursed through RAMQ by submitting claims for medical services provided. This file contains the date of service, where the service was dispensed, one diagnosis coded with ICD-9, medical procedures provided,

cost of the service, as well as, specialty and identification of the treating physician. These databases can be linked between one and another using the HCIN.

The MED-ECHO database contains information on all admissions to acute care hospitals in Quebec. It contains the HCIN, the date of admission, length of stay, and diagnoses coded with ICD-9/ICD-10 codes; admission and principal & secondary diagnoses. The RAMQ and MED-ECHO databases can also be linked using the HCIN.

The reMed database contains data on medications dispensed in community pharmacies to a sample of patients with private drug insurance. The reMed contains the HCIN, the private insurance policy number (PIPN), the type of insurance plan (co-payment, annual premium, and so on), the name, dose formulation and quantity of the medication dispensed, the date the medication was dispensed, the pharmacy & the prescriber's encoded identifier, the cost of medications, and the amount reimbursed by the insurer. The drug related variables recorded in reMed are almost identical to the variables recorded in the RAMQ Prescription Medications file. The HCIN allows the linkage of the reMed to the RAMQ and MED-ECHO databases.

Methods

After having obtained the authorization from the research ethics committee of the CIUSSS du Nord-de-l'île-de-Montréal and from the director of Professional Services, all the charts of patients who received anti-IL-5/IL5R inhibitors at the tertiary asthma clinic of *the Hôpital du Sacré-Coeur de Montréal* will be reviewed.

A response to treatment will be defined by a 50% reduction in the number of asthma exacerbations in the year following the initiation of anti-IL-5/IL5R inhibitors compared to the year preceding the initiation of the treatment or a 50% decrease in the OCS doses for steroid dependent patients.

A functional response to treatment will also be assessed in the Tertiary asthma clinic cohort. An improvement of FEV₁ of 12 % and ≥ 200 ml will be considered as clinically significant.

Asthma exacerbations will be defined by a short treatment with systemic corticosteroids (less than 14 days), visit to the emergency department or hospitalization related to asthma. If two markers of an asthma exacerbation occurred with 14 days, they will be counted as only one exacerbation. This definition will be applied in the Tertiary asthma clinic cohort and the population-based cohort.

The potential predictors of response to treatment will be collected in the Quebec registry in respiratory health (RESP) database and or the medical charts: age (continuous), sex (women/men), atopy (atopic/non atopic), body mass index (continuous), smoking habits (current or ex/never smokers)(never/ever/current), percent predicted FEV₁, asthma treatment (dose of ICS, dose of OCS if any), exacerbation rate in the year preceding treatment initiation, blood eosinophil count, and sputum eosinophil count.

The Quebec Registry in Respiratory Health (RESP) is a database originally built in 2010 by [name]. This registry aims to store clinical and functional data in subjects with asthma and COPD followed at the *Hôpital du Sacré-Coeur de Montréal* or at the *Centre Hospitalier Universitaire de Sherbrooke*. The patients included in the database have also consented to have their clinical data matched to the *Régie de l'assurance médicale du Québec* (RAMQ) and *Maintenance et exploitation des données pour l'étude de la clientèle hospitalière* (MED-ECHO) administrative databases and the reMed database on medications for patients with private health insurance plans which enables access to data on medical services, hospitalisations and medications dispensed by pharmacies. This databases allows us to collect the following variables: age, sex, area of residence (rural or urban), treatment (if insured with the RAMQ), comorbidities, visits to the physician for asthma and all causes, visits to the emergency for asthma and any other medical issues, and hospitalization for asthma and any other medical issues.

This database allows us to assess the adherence to inhaled corticosteroids (ICS) by calculating the proportion of days covered (PDC) (11), a measure of adherence based on prescription claims data. The PDC is defined as the sum of the duration of all prescriptions of ICS filled over one year, divided by 365 days, expressed in percentages. The PDC will be estimated using prescription refill

data obtained from the RAMQ and reMed databases in the year preceding and following cohort entry.

Potential response predictors to treatment will also be collected in the RAMQ and reMed databases: age (continuous), sex (women/ men), type of asthma treatment (ICS, long-acting beta 2 agonists (LABA), Long-acting muscarinic antagonists (LAMA), Leukotriene-receptor antagonist (LTRA), omalizumab, or OCS if any), adherence to asthma treatment before and after cohort entry, comorbidities as measured by the Charlson score before and after cohort entry, exacerbation rate in the year preceding cohort entry, and area of residence (rural or urban) at cohort entry.

We shall require the authorization from *the Commission d'accès à l'information du Québec* to obtain the RAMQ and MED-ECHO data on healthcare utilization and medication for all subjects who have been diagnosed with asthma and who have been receiving anti-IL-5/IL5R inhibitors between January 2016 and June 2020; for example, subjects included in the tertiary asthma clinic cohort and the population-based cohort.

We will require from the RAMQ and MED-ECHO, the data on visits to the physicians, visits to the emergency departments, and hospitalizations for asthma and any other medical issues as well as the use of medication of all patients who have been diagnosed with asthma as defined by a validated operational definition(12) – 2 ambulatory visits for asthma or an hospitalization for asthma within the past 2 years a – in the year preceding the prescription of anti-IL-5/IL5R inhibitors and who have been receiving anti-IL-5/IL5R inhibitors from January 2016 to June 2020 in the Province of Quebec. We will request the data from January 2014 to June 2021.

Statistical analysis

We will estimate the proportion and confidence interval of patients' responder to anti-IL-5/IL5R inhibitors in the Tertiary asthma clinic cohort and the population-based cohort.

A logistic regression model will be used to identify the response predictors to anti-IL-5/IL5R inhibitors. Variable selection will be made with the Lasso selection procedure (13).

We will perform a Poisson regression model to compare the exacerbation rate in the year before and after the treatment initiation with anti-IL-5/IL5R inhibitors in the tertiary asthma clinic cohort and the population-based cohort. We will include all patients who received anti-IL-5/IL5R inhibitors in the analysis. The duration of follow-up will be taken into account using an offset in the Poisson regression model.

We will perform a linear regression model to compare the OCS doses in the year before and after the treatment initiation with anti-IL-5/IL5R inhibitors in the tertiary asthma clinic cohort and the population-based cohort.

Sample size and statistical power

To fulfill the primary objective

With 60 patients in the Tertiary asthma clinic cohort and an expected response rate of 50% we will have the power to identify 6 predictors (14). With 570 patients in the population-based cohort and an expected response rate of 50% we will have the power to identify more than 50 predictors (14).

With 60 patients in the tertiary asthma clinic cohort, an expected rate of 1.48 exacerbations per year per patient (3), and an alpha error of 5%, we will have a power of 80% to show a reduction of 50% in the rate of exacerbation (1 year post- anti-IL-5/IL5R inhibitors versus 1 year pre- anti-IL-5/IL5R inhibitors). With 570 patients in the population-based cohort and the same assumptions, we will have more than 90% power to show a reduction of 50% in the rate of exacerbation (1 year post- anti-IL-5/IL5R inhibitors versus 1 year pre- anti-IL-5/IL5R inhibitors).

Limitations

Fifty eight percent of Quebecers are covered by a private drug insurance. With reMed, we will be able to obtain this data for only a small sample of patients with a private drug insurance plan.

Perspective:

Up to date, the main prognostic factor identified in subjects treated with anti-IL5 is the level of eosinophilic inflammation. However, this factor has been identified in subjects enrolled in clinical trials. It is unknown whether, smoking, co-morbidities or adherence to ICS affects the response to anti-IL-5/IL5R inhibitors. This study will be the first to answer this question in both a selected population followed in a tertiary asthma clinic and in a large population from Quebec.

Schedule of Activities

Study Procedures	Estimated Date
Ethic committee submission	November 2020
Submission to the Commission d'accès à l'information du Québec/RAMQ	December 2020
Clinical Data collection from RESP and hospital charts.	December 2020
First data analysis for clinical data And RAMQ data reception	March 2021
Submission of an abstract to the ATS	November 2021
Data Analysis	September 2021
Report and article writing	October 2021

References

1. Canada Go. Fast facts about asthma: Data compiled from the 2011 Survey on Living with Chronic Diseases in Canada

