The majority of patients receiving anti-IL-5/IL5R inhibitors will have at least a 50% decrease in their asthma exacerbations rate in a tertiary clinic specialized in the field of severe asthma.

The level of blood and sputum eosinophils will be the main response predictor to anti-IL-5/IL5R inhibitors in a tertiary clinic specialized in the field of asthma whereas the rate of exacerbation in the year prior to the initiation of anti-IL-5/IL5R inhibitors will be the main predictor of asthma exacerbations in a non-selected population of severe asthmatics in Quebec.

Primary Objectives

1. To assess and compare the response* to treatment before and after the initiation of anti-IL-5/IL5R inhibitors in patients followed in a tertiary asthma clinic from the Province of Quebec and in a non-selected population of asthmatic subjects covered by the *Régie de l'Assurance Maladie du Québec*'s (RAMQ) public drug insurance plan or by a private drug insurance.
2. To assess the clinical response predictors to anti-IL-5/IL5R inhibitors in a cohort of severe asthmatics followed in tertiary care as well as in a non-selected population of asthmatic subjects covered by the RAMQ's public drug insurance plan *or by a private drug insurance*.

* Response to treatment will be defined by a reduction of asthma exacerbations of at least 50% *and* or a 50% or higher reduction of the OCS doses in steroid dependent patient compared to the year prior to treatment initiation.

Secondary objectives:

1. To assess the mean reduction of exacerbation in both cohorts.
2. To assess the adherence and persistence to treatment with anti-IL-5/IL5R inhibitors and ICS after treatment initiation with anti-IL-5/IL5R inhibitors..

Study populations.

A) A Tertiary asthma clinic cohort of patients 18 years and older who are followed at the outpatient asthma clinic of Sacre-Cœur Hospital and who have been treated with anti-IL-5/IL5R inhibitors between January 2016 and June 2020 and are included in the reMed database;

We will ensure that those patients had severe eosinophilic asthma inadequately controlled on high dose ICS plus additional controlled therapy and had a blood eosinophil count of 150 cells/ μ L on initiation or 300 cells/ μ L in the past 12 months and had either 2 or more significant asthma exacerbations in the past 12 months or were treated with daily oral steroids

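### The primary response outcome joins its two criteria with *and* in one section and *or* in another, and nothing says which rule governs steroid-dependent patients

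*Combined protocol and SAP*

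**What the plan says.** Three places define response.

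- **Outcomes, Objective 1, primary outcome:** "a reduction of asthma exacerbations of at least 50% and a 50% or higher reduction of the OCS doses in steroid dependent patients", comparing the year after initiation with the year before.
- **Methods, response definition:** an exacerbation reduction of 50% "compared to the year preceding the initiation of the treatment or a 50% decrease in the OCS doses for steroid dependent patients".
- **Primary Objectives, footnote:** "asthma exacerbations of at least 50% *and* or a 50% or higher reduction of the OCS doses".

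No section ranks these. The Objective 2 outcome uses the term without a rule ("Objective 2: Response to anti-IL-5/IL5R inhibitors in the tertiary asthma clinic cohort and in the population-based cohort"). The Statistical analysis section estimates the responder proportion with a confidence interval and then states: "A logistic regression model will be used to identify the response predictors to anti-IL-5/IL5R inhibitors". It does not restate a definition. The Hypothesis concerns the exacerbation criterion alone.

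Steroid-dependent patients are part of the intended population. Under Study populations, daily oral steroids are an alternative to two or more exacerbations in the previous year, both for the tertiary cohort and in the reimbursement criteria.

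**The concern.** Patients who are not steroid-dependent can be judged only on exacerbations, so the connective does not touch them. For steroid-dependent patients it decides the class of everyone who meets one criterion but not the other.

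Two programmers could each follow the protocol faithfully and produce different responder variables. The primary proportion would differ, and so would the dependent variable of the logistic/Lasso model. The study is retrospective, so the events have already happened when the rule is chosen. A choice left open until then could be guided by the result, although nothing in the documents suggests that it was.

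A reader could not recover the other answer from the planned reports. The Objective 1 secondary outcomes are "Exacerbation rates and OCS doses (for steroid-dependent patients) in the year preceding and following initiation of anti-IL-5/IL5R inhibitors", that is, rates and doses. They do not include the proportion of patients meeting each 50% criterion.

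**Working it through.** **1. The wordings side by side.** For a steroid-dependent patient three rules are open. Outcomes, read plainly, requires both criteria. Methods, read plainly, accepts either. Outcomes can also be read distributively, with the exacerbation criterion for patients generally and the OCS criterion for steroid-dependent patients, which gives OCS alone.

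| Exacerbation criterion | OCS criterion | Both | Either | OCS alone |
|---|---|---|---|---|
| met | met | responder | responder | responder |
| met | not met | non-responder | responder | non-responder |
| not met | met | non-responder | responder | responder |
| not met | not met | non-responder | non-responder | non-responder |

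The two middle rows are where the definitions part.

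The footnote is the weakest evidence. Its double connective may simply mean and/or, as it appears to in the Methods phrase "registry in respiratory health (RESP) database and or the medical charts". It would then agree with Methods, and the section labelled primary outcome would be the odd one out. The document does not say so.

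**2. The plan's own figure.** The Sample size section assumes "an expected response rate of 50% we will have the power to identify 6 predictors" with 60 patients, and the same rate with 570. That implies 60 × 0.50 = 30 and 570 × 0.50 = 285 responders. The 50% is an overall rate and is tied to no rule, so it cannot show which definition was meant.

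**3. Illustration of size.** The documents give no steroid-dependent share *s*, no component rates and no correlation φ between the criteria. All of these are assumptions here. Take 50% meeting each criterion.

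- P(both) = 0.5 × 0.5 + φ × 0.25 = 0.25 + 0.25φ
- P(either) = 0.5 + 0.5 − P(both) = 0.75 − 0.25φ
- P(OCS alone) = 0.50
- Overall proportion = (1 − s) × 0.50 + s × P(rule)
- Gap, either minus both = s × 0.5 × (1 − φ)

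| s | Both (φ = 0) | OCS alone | Either (φ = 0) | Gap, φ = 0 | Gap, φ = 0.5 |
|---|---|---|---|---|---|
| 10% | 47.5% | 50% | 52.5% | 5 points | 2.5 points |
| 30% | 42.5% | 50% | 57.5% | 15 points | 7.5 points |
| 50% | 37.5% | 50% | 62.5% | 25 points | 12.5 points |

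At φ = 0 the gap is 3, 9 or 15 of 60 patients, and 28.5, 85.5 or 142.5 of 570. It is zero at φ = 1 or s = 0.

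With s = 30% and φ = 0, the Wilson 95% intervals at n = 570 are 38.5% to 46.6% (both) and 53.4% to 61.5% (either). They do not overlap and they lie on opposite sides of 50%. At n = 60 they are 30.8% to 55.1% and 44.9% to 69.2%, which overlap.

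**4. Sensitivity to the assumed rate.** With equal rates *p* and independence, the gap among steroid-dependent patients is 2p(1 − p). This is largest at p = 0.5, where it is 0.50. At p = 0.8 it is 2 × 0.8 × 0.2 = 0.32, so at s = 30% the overall gap falls from 15 to 0.30 × 32 = 9.6 points.

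**The case against.** The strongest reply is that Methods can be read distributively too: exacerbations for patients in general, OCS dose for those who are steroid-dependent. Both sections would then state the same rule and the contradiction would be only apparent. That reading is possible, but no section states it, and it is one of several. It shows that the rule is unsettled rather than settling it.

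Other points have some force:

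- The Poisson model for exacerbation rates, the linear model for OCS doses and the power statements for the rate comparison do not depend on the connective. This is true, and it limits the problem to the responder proportion and the predictor model. Those carry the primary outcome and Objective 2.
- Objective 2 would naturally inherit the Objective 1 definition. Agreed; it inherits the same conflict and is not a separate omission.
- The illustration is hypothetical and uses the rate that makes the gap largest under independence with equal rates. This stands. The case rests on the text, not on these numbers.
- The counts use 60 and 570, whereas Target enrolment gives 100 in the clinic and about 1160 plus 100 in the population cohort. The percentage-point gaps do not change. With those sizes, 5 to 25 points would be 5 to 25 of 100 patients and 63 to 315 of 1260.
- The entry criteria make a zero exacerbation count before treatment likely mainly among those entering on daily steroids. This is fair, and it makes zero counts a secondary clarification.

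**Conclusion.** The concern holds. The section labelled primary outcome and the Methods section give different rules on their plain wording, the footnote does not resolve them, and no order of precedence is stated. Both primary objectives depend on the answer, so this must be fixed.

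The size cannot be established from the documents. With 50% meeting each criterion and 10% to 50% of patients steroid-dependent, the overall responder proportion moves by 5 to 25 points under independence and by 2.5 to 12.5 points at a correlation of 0.5. It does not move if the criteria coincide or nobody is steroid-dependent.

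Two gaps in the same rule are secondary. Steroid dependence is not defined for the purpose of response: the reimbursement criteria mention both daily oral steroids and a course of three months or more, and neither is linked to the rule. A percentage reduction from a count of zero before treatment is also undefined. Such a patient could not meet the exacerbation criterion when both are required, but could still respond through the OCS criterion when either suffices.

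**What to change.** Reconcile the Primary Objectives footnote, the Outcomes section and the Methods section to one rule before the response variable is derived. If outcome data have already been examined, record when the rule was chosen.

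- Write the rule separately for steroid-dependent and other patients. For the former, say whether both criteria, either criterion or the OCS criterion alone is required. The choice is the sponsor's.
- State that the same rule defines the Objective 2 outcome, and which rule the 50% planning rate refers to.
- Report the alternative rule as a sensitivity analysis.
- Report the proportion meeting each component separately. The exacerbation component alone answers the stated hypothesis.
- Within the rule, say how steroid dependence is identified in each cohort and how a pre-treatment exacerbation count of zero is classified, and report how many patients have one.

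The cost is wording in three places and one sensitivity table. No extra patients or data are needed.

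### Population-based cohort: ICS adherence in the year after treatment start is offered as a predictor of response in that same year, so a consequence of response could be selected as a predictor

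*Combined protocol and SAP*

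**What the plan says.** Under Outcomes, Objective 2 is response "in the population-based cohort in the year following initiation of anti-IL-5/IL5R inhibitors". The population-based list under Potential Predictors includes "adherence to ICS in the year before and after treatment initiation with anti-IL-5/IL5R inhibitors". In the same list, the type of asthma treatment and the exacerbation rate are dated to the year before initiation only.

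Methods confirms the post-entry window. The PDC is to be estimated from refill "data obtained from the RAMQ and reMed databases in the year preceding and following cohort entry", and the RAMQ and reMed predictors include "adherence to asthma treatment before and after cohort entry, comorbidities as measured by the Charlson score before and after cohort entry". The Potential Predictors section does not list the Charlson score at all, and Methods gives no length for its window.

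Statistical analysis states: "A logistic regression model will be used to identify the response predictors to anti-IL-5/IL5R inhibitors". It adds: "Variable selection will be made with the Lasso selection procedure". It gives no timing restriction on candidates, no landmark, and no separate explanatory model. Secondary objective 2 already treats ICS adherence after initiation as something to be described in its own right.

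**The concern.** A predictor of response should be known when treatment starts. Post-entry ICS adherence is not known then, and it accumulates over the same months in which response is determined. A patient who improves may refill less; one who does not improve may refill more, or stop. Either way the association can run from outcome to supposed predictor, and Lasso cannot tell the two directions apart.

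Identifying predictors is a primary objective, and the Perspective section makes adherence and co-morbidity headline questions: "It is unknown whether, smoking, co-morbidities or adherence to ICS affects the response to anti-IL-5/IL5R inhibitors". As written, a fall in refilling after improvement could be published as evidence that lower adherence predicts response. The damage also spreads: putting post-entry adherence in the model distorts the coefficient of pre-entry adherence, which is a legitimate candidate.

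The post-entry Charlson score has the same timing fault. Asthma admissions count as exacerbations and also generate coded diagnoses, so the two may be linked, but the documents do not allow that link to be sized.

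**Working it through.** **Windows.** Outcome: months 0–12 after entry (Outcomes, Objective 2). Post-entry PDC: months 0–12 after entry (Potential Predictors; Methods). The overlap is complete. The plan has no figure of its own to reproduce here.

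**Inputs for the illustration.** From Sample size and statistical power: N = 570 and 50% response. Assumed, because the documents are silent: PDC standard deviation 25 points; pre/post correlation ρ = 0.6; no causal effect of adherence on response; post-entry PDC lowered in responders by d = 0, 1, 2, 5 or 10 points. The simulations used 13 candidates, with response depending only on prior exacerbation rate (log-odds 0.5 per SD).

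**Step 1: unadjusted comparison.** z = (d/25) / (2/√570). For d = 5: 0.2 / 0.0838 = 2.387. Two-sided 5% rejection is Φ(z − 1.96) + Φ(−z − 1.96).

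**Step 2: Lasso.** 10-fold cross-validation, 200 runs per shift.

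**Step 3: unpenalised adjusted logistic model.** 2,000 runs per shift.

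| Shift d (points) | 0 | 1 | 2 | 5 | 10 |
|---|---|---|---|---|---|
| z, unadjusted | 0 | 0.477 | 0.955 | 2.387 | 4.775 |
| Post-entry PDC flagged, unadjusted | 5% | 8% | 16% | 67% | 99.8% |
| Post-entry PDC selected, Lasso, minimum-error penalty | 17% | 28% | 38% | 88% | 100% |
| Post-entry PDC selected, Lasso, one-SE penalty | 2% | 4% | 7% | 50% | 99.5% |
| Post-entry PDC significant, adjusted | 5% | 10% | 21% | 81% | 100% |
| Pre-entry PDC (no true effect) significant, post-entry PDC in model | 5% | 6% | 11% | 43% | 92% |

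With post-entry PDC left out, pre-entry PDC is significant in 5–6% at every shift, which is about the nominal rate.

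**Step 4: closed-form check of the spill-over.** Take two normal predictors with within-group correlation ρ and a shift of δ SD in the post-entry one only. The log-odds per SD are then −δ/(1 − ρ²) for post-entry and +ρδ/(1 − ρ²) for pre-entry PDC, each with standard error about 1/√(N × 0.25 × (1 − ρ²)). With δ = 5/25 = 0.2 and ρ = 0.6:

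- Post-entry: −0.2/0.64 = −0.3125, odds ratio exp(−0.3125) = 0.73.
- Pre-entry: 0.6 × 0.2/0.64 = 0.1875, odds ratio 1.21, although the true value is 1.
- Standard error: 1/√(570 × 0.25 × 0.64) = 0.1047.
- z = 2.98 and 1.79; rejection 85% and 43%.

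These agree with the simulated 81% and 43%. A separate two-predictor simulation (500 runs) gave 84% and a median odds ratio of 0.73 for post-entry PDC at the same shift.

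**Step 5: sensitivity.** At d = 5, the false-significance rate for pre-entry PDC runs from 11% (ρ = 0.3) to 86% (ρ = 0.8). Reversing the shift, so that responders refill more, gave 83% for post-entry and 43% for pre-entry PDC. The problem does not depend on direction.

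**Lesser point: the PDC formula.** Methods says: "The PDC is defined as the sum of the duration of all prescriptions of ICS filled over one year, divided by 365 days". Nothing caps this sum. Thirteen 30-day fills give 13 × 30/365 = 106.8%, and two ICS products each filled all year give 2 × 365/365 = 200%.

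**The case against.** The strongest reply is that the inclusion is deliberate. The Perspective section asks whether adherence affects response, which is an explanatory question, and adherence during treatment is relevant to it. In an uncontrolled pre-post study, a change in ICS use after entry is also a rival explanation for fewer exacerbations, and dropping the variable would remove the plan's only stated handle on it. This stands as a reason to keep a post-entry analysis, but not to place the variable in the predictor model. The plan never separates the two uses, and an association measured over the same months cannot show direction.

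The numbers can also be challenged. Every shift, the SD and the correlation are assumed, and nothing in the documents says that responders refill less. The plan names no Lasso penalty rule, and the rule matters: 88% or 50% at 5 points, and only 4–7% at 1–2 points under the one-SE rule. The 43% for pre-entry PDC comes from an unpenalised model. A 100-run check under Lasso at 5 points selected pre-entry PDC in 42% at minimum error (21% with no shift) and 8% at one SE (0% with no shift). All of this is fair. The figures show that the design is vulnerable, not how large the bias will be.

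Finally, the Charlson score appears in only one of the two predictor lists, and the documents do not say how it treats asthma codes, so only the timing objection to it is firm. The PDC formula is a separate measurement issue and does not support the main point.

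**Conclusion.** The plan is wrong as written. Two sections offer post-entry ICS adherence as a predictor of an outcome measured over the same year, and nothing elsewhere restricts or relabels it. That conclusion rests on the text alone.

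The size and direction of any bias are unknown. Under the stated assumptions, a 5-point PDC shift caused by response is enough for post-entry adherence to be selected in half or more of studies, and a 10-point shift makes selection nearly certain. Shifts of 1–2 points matter little under the one-SE penalty. The spill-over onto pre-entry adherence is real but depends on the correlation and on the penalty rule.

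The reach is limited to the population-based part of Objective 2. The responder proportions, the Poisson comparison of exacerbation rates, the OCS dose comparison and the tertiary-clinic predictor list are unaffected. This should be fixed before the predictor models are run.

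**What to change.** 1. In Potential Predictors and in Methods, remove the post-entry period from the candidate predictors. State once, under Statistical analysis, that candidates in the response-predictor models are limited to information available up to cohort entry.
2. Use ICS adherence in the year before entry and a pre-entry Charlson score with a stated look-back. Data are requested from January 2014, two years before the earliest possible entry. Make the two predictor lists agree on whether the Charlson score is included.
3. Report post-entry ICS adherence under secondary objective 2. To keep the Perspective question, and to examine changed ICS use as a rival explanation, add a separately labelled association with response that is not interpreted as prediction.
4. Lesser change: define the PDC as distinct days with any ICS supply within the window, divided by days observed. RAMQ coverage and death dates supply the denominator for the public sub-cohort. The description of reMed under Source of data lists no coverage dates, so a denominator rule must be stated for it.

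The cost is wording and a small amount of programming, because the pre-entry variables are already planned. The price is that on-treatment adherence is no longer a candidate in the predictor model; item 3 keeps it in the report.
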